6.4 Analysis Methods

The family-wise type I error rate (FWER) will be controlled at a 0.05 significance level for primary and major secondary endpoints using a prespecified graphical procedure (see Section 6.6). Unless otherwise specified, all other hypothesis testing will be conducted at a nominal significance level of 0.05.

For assessments of the primary endpoint and other binary efficacy and health outcomes endpoints, the following will be provided unless otherwise specified:

- Observed percentage for each treatment group along with the corresponding 2-sided 95% confidence interval (CI)
- The difference in percentages and 95% CI using the Newcombe-Wilson method without continuity correction, used for descriptive purposes
- The p-value and 95% (unless otherwise specified) CI for the odds ratio from the logistic regression model, used for primary statistical inference. The model will include the following explanatory variables: treatment, baseline disease activity (total SLEDAI-2K <10; ≥ 10), baseline corticosteroid dose (<10 mg/day; ≥ 10 mg/day prednisone or equivalent) and region (North America, Central/South America/Mexico, Europe, Asia and Rest of World). A Firth penalized likelihood will be used (Firth 1993), and
- If deemed necessary, additional analyses of categorical efficacy variables will be conducted to address sparse data or small sample sizes. The Fisher's exact test will be utilized if necessary.

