Treatment comparisons of continuous efficacy and health outcome variables, except for SLICC/ACR Damage Index, Patient's Global Impression of Change and Joint Stiffness Duration, will use a restricted maximum likelihood-based MMRM analysis. The model will include the following explanatory variables as fixed factors: treatment, baseline disease activity (total SLEDAI-2K <10; ≥ 10), baseline corticosteroid dose (<10 mg/day; ≥ 10 mg/day prednisone or equivalent), region (North America, Central/South America/Mexico, Europe, Asia and Rest of World), visit (as categorical variable), baseline value, treatment-by-visit interaction, and baseline value-by-visit interaction. The response variable will be change from baseline across postbaseline visits. Within-patient errors will be modeled using an unstructured covariance structure. If the model fails to converge, the following covariance structures will be implemented in the following order: heterogeneous Toeplitz, heterogeneous autoregressive (1) heterogeneous compound symmetry, and autoregressive. The least squares (LS mean) difference, standard error, p-value, and CIs will be reported. Type III tests for the LS means will be used for the statistical comparisons.

Treatment comparisons of SLICC/ACR Damage Index will be made using analysis of covariance (ANCOVA) with baseline value as covariate. For Patient's Global Impression of Change, the analysis of variance (ANOVA) will be applied. For both models, treatment, baseline disease activity (total SLEDAI-2K <10; ≥ 10), baseline corticosteroid dose (<10 mg/day; ≥ 10 mg/day prednisone or equivalent), and region (North America, Central/South America/Mexico, Europe,

Asia and Rest of World) will be included as the categorical factors. Type III tests for LS means will be used for statistical comparison between treatment groups. The LS mean difference, standard error, p-value, and 95% CI may also be reported.

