6.4.2.1 Non-responder Imputation (NRI)

The non-responder imputation (NRI) method may be used when the estimand of interest uses the composite strategy (EMA 2020) for handling intercurrent events. In this strategy, patients will be considered non-responders for the NRI analysis if they do not meet the clinical response criteria or have missing clinical response data (based on each set of [Table JAIA.6.5](#)) at the analysis time point.

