Abbreviations: ACR = American College of Rheumatology Damage Index; BILAG = British Isles Lupus Activity Group; BICLA = British Isles Lupus Assessment Group Based Composite Lupus Assessment; CLASI = Cutaneous Lupus Erythematosus Disease Area and Severity Index; CNS = Central Nervous System; EQ-5D-5L = European Quality of Life–5 Dimensions–5 Level; FACIT = Functional Assessment of Chronic Illness Therapy; LLDAS = Lupus Low Disease Activity State; MCS= Mental Component Score; NRS = Numeric Rating Scale; PCS= Physical Component Summary; PGA = Physician's Global Assessment of Disease Activity; SF-36 = Short Form 36; SFI = SLEDAI Flare Index; SLE = Systemic Lupus Erythematosus; SLICC = Systemic Lupus International Collaborating Clinics; SRI-4 = SLE Responder Index; SLEDAI-2K = Systemic Lupus Erythematosus Disease Activity Index 2000; UK = United Kingdom; US = United States; VAS = visual analogue scale; WPAI:Lupus = Work Productivity and Activity Impairment – Lupus.

Note: Additional supplemental and sensitivity analyses are described in Section 6.10.3.3.

The datapoint sets are defined to estimate the estimands in [Table JAIA.6.5](#). The mITT population will be included in the analysis according to the treatment they were randomized, unless otherwise specified in [Table JAIA.6.6](#).

Patients who are imputed as nonresponders due to a qualifying intercurrent event for binary categorical efficacy variables, will be defined as such from the time of qualifying event, plus 1 day, onward.

Table JAIA.6.5. Datapoint Sets for Use in Efficacy/Health Outcomes Analyses

Datapoint sets	Definition of Missing Data Due to ICEs	Estimand of Interest

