SLICC/ACR	Change from baseline in SLICC/ACR	ANCOVA with mLOCF	PP	Week 52 visit	Exploratory endpoint
SF-36 V2 acute	Change from baseline in MCS	MMRM	PP	Week 52 visit	Secondary endpoint
	Change from baseline in physical component score (PCS)	MMRM	PP	Week 52 visit	Secondary endpoint
	Change from baseline in domain scores SF-36 health survey version 2 acute	MMRM	PP	Week 52 visit	Secondary endpoint
EQ-5D-5L	Change from baseline in EQ-5D-5L US/UK population-based index scores and VAS	MMRM	PP	Week 52 visit	Secondary endpoint
	Proportion of patients with no problem in each EQ-5D-5L item score	Logistic Regression, NRI	PP	Week 52 visit	Secondary endpoint

Description of Efficacy/Health Outcomes Analyses

Measure	Variable	Analysis and Imputation Method	Datapoint Sets	TPI*	Analysis Type
WPAI-Lupus	Change from baseline in WPAI-Lupus ⁱ	MMRM	PP	Week 52 visit	Secondary endpoint

Abbreviations: AC = as collected; ACR = American College of Rheumatology Damage Index; ANCOVA = analysis of covariance; ANOVA = analysis of variance; BICLA = British Isles Lupus Assessment Group Based Composite Lupus Assessment; BILAG = British Isles Lupus Activity Group; CLASI = Cutaneous Lupus Erythematosus Disease Area and Severity Index; EQ-5D-5L = European Quality of Life-5 Dimensions-5 Level; FACIT = Functional Assessment of Chronic Illness Therapy; LLDAS = Lupus Low Disease Activity State; MCS = mental component score; MI = multiple imputation; mITT = modified intent-to-treat; mLOCF = modified last observation carried forward; MMRM = mixed model for repeated measures; NRI = non-responder imputation; NRS = Numeric Rating Scale; PCS = Physical Component Summary; PGA = Physician's Global Assessment; PP = per protocol; PPCV = per protocol COVID free; SFI = SLEDAI Flare Index; SLE = Systemic Lupus Erythematosus; SLEDAI-2K = Systemic Lupus Erythematosus Disease Activity Index 2000; SF-36 = Short Form 36; SRI-4 = SLE Responder Index; SLICC = Systemic Lupus International Collaborating Clinics; TPI = time point of interest; UK = United Kingdom; US = United States; VAS = visual analogue scale; WPAI-Lupus = Work Productivity and Activity Impairment Questionnaire: Lupus V2.0.

- ^a Population is a subset of mITT which includes patients with SLEDAI-2K score $\geq x$ at baseline (where x is 5, 6, 7, 8) for each SRI-x responder analysis.
- ^b Population is a subset of mITT which includes patients with SLEDAI-2K score >0 within the organ domain at baseline.

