- ^c Population is a subset of mITT which includes patients with at least one SLEDAI-2K item = 0 in the organ domain at baseline.
- ^d Population is a subset of mITT which includes patients with BILAG A or B in the organ domain at baseline.
- ^e Population is a subset of mITT which includes patients without BILAG A in the organ domain at baseline.
- ^f Population is a subset of mITT which includes patients with CLASI total activity score ≥ 10 at baseline.
- ^g Population is a subset of mITT which includes patients with > 7.5 mg/day prednisone at baseline. The logistic regression model covariates include treatment groups, baseline disease activity (total SLEDAI-2K <10 ; ≥ 10) and region (North America, Central/South America/Mexico, Europe, Asia and Rest of World).
- ^h Population is a subset of mITT which includes patients with > 0 mg/day prednisone at baseline.
- ⁱ For absenteeism score, presenteeism score, and work productivity loss score, population is a subset of mITT which includes patients who had employment status of Yes at baseline.
- * Assessments collected at multiple visits will be analyzed at each visit, in addition to the primary time point listed in the table.

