Corticosteroid used ^d See Section 6.9.1 for details of prednisone (or equivalent) baseline dose	Yes	Yes, No <10 mg/day or ≥10 mg/day ≤7.5 mg/day or >7.5 mg/day
Immunosuppressant ^d use at baseline	No	Yes, No
Mycophenolate use at baseline	No	Yes, No
Azathioprine ^d use at baseline	No	Yes, No
Methotrexated use at baseline	No	Yes, No
Antimalarial ^d use at baseline	No	Yes, No
Hydroxychloroquine use at baseline	No	Yes, No
NSAID ^d use at baseline	No	Yes, No
Statin use at baseline	No	Yes, No
Other Baseline Measures		
Baseline SF-36 PCS, MCS	Yes	None
Baseline WPAI Lupus – Employment status	No	Yes, No
Baseline WPAI Lupus – Absenteeism score, Presenteeism Score, Work productivity Loss Score, Activity Impairment Score.	Yes ^e	None
Baseline QIDS-SR16 score	Yes	<11, ≥11 None (0 – 5), Mild (6 – 10), Moderate (11 – 15), Severe (16 – 20), Very severe (21 – 27)
EQ-5D-5L VAS and Item scores	Yes	None
FACIT-Fatigue Total score	Yes	None

Variable	Continuous Summary	Categorical Summary ^a
Worst Pain NRS	Yes	None
Worst Joint Pain NRS	Yes	None
Worst Fatigue NRS	Yes	None

Abbreviations: ACR = American College of Rheumatology Damage Index; ANA = antinuclear antibodies; anti-dsDNA = anti-double stranded DNA; BILAG = British Isles Lupus Assessment Group; BMI = body mass index; CLASI = Cutaneous Lupus Erythematosus Disease Area and Severity Index; eGFR = estimated glomerular filtration rate; EQ-5D-5L = 5-level EQ-5D version; FACIT = Functional Assessment of Chronic Illness Therapy; IgA = immunoglobulin A; IgG = immunoglobulin G; IgM = immunoglobulin M; LLN = lower limit of normal; MCS = Mental Component Summary; NRS = Numeric Rating Scale; NSAID = nonsteroidal anti-inflammatory drug; PCS = Physical Component Summary; QIDS SR-16 = Quick Inventory of Depressive Symptomatology; SELENA = Safety of Estrogens in Lupus Erythematosus National Assessment; SF-36 = Short Form 36; SLE = Systemic Lupus Erythematosus; SLEDAI-2K = Systemic Lupus Erythematosus Disease Activity Index 2000; SLICC = Systemic Lupus International Collaborating Clinics; VAS = Visual Analog Scale; WPAI = Work Productivity and Activity Impairment.

- a This column specifies the levels of the categorical variable to be summarized.

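### The EQ-5D-5L 'no problem' analyses leave out the baseline level of the same item, which costs precision in five secondary comparisons per dose

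*SAP*

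**What the plan says.** The EQ-5D-5L block of SAP Table JAIA.6.6 has two rows. The first is change from baseline in the index scores and VAS, by MMRM. The second is "Proportion of patients with no problem in each EQ-5D-5L item score", by logistic regression with NRI on the PP datapoint set at the Week 52 visit, labelled a secondary endpoint. Table JAIA.6.4 gives each of the five dimensions five levels, with level 1 the best.

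- **Population.** The default in Section 6.10.1 is "The mITT population will be included in the analysis according to the treatment they were randomized, unless otherwise specified in" Table JAIA.6.6. The item row carries no footnote, so the whole mITT population is analysed. Other binary rows are restricted by baseline status, for example CLASI: "Population is a subset of mITT which includes patients with CLASI total activity score ≥ 10 at baseline".
- **Model.** For binary endpoints Section 6.4 states: "The model will include the following explanatory variables: treatment, baseline disease activity (total SLEDAI-2K <10; ≥ 10), baseline corticosteroid dose", followed by region. No baseline value of the endpoint enters. The MMRM in the same section does include "baseline value, treatment-by-visit interaction, and baseline value-by-visit interaction".
- **Availability.** Appendix 2 lists "EQ-5D-5L VAS and Item scores" among the baseline measures.
- **Missing data.** Under Section 6.4.2.1 patients are non-responders "if they do not meet the clinical response criteria or have missing clinical response data" at the time point.

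Table JAIA.4.1 names the EQ-5D-5L endpoint only as change from baseline at Week 52, among the other secondary endpoints without multiplicity control.

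**The concern.** Being at 'no problem' at Week 52 is a state. A patient at level 1 at both baseline and Week 52 counts the same as one who moved from level 4 to level 1. Where an item has many patients at level 1 at baseline, the baseline level should help to predict the Week 52 level. A logistic model without it leaves that variation unexplained, and chance differences between arms in the starting level then add noise to the treatment comparison.

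The SAP avoids this in the neighbouring EQ-5D row, where the MMRM adjusts for the baseline value. For the item row it neither adjusts nor says that the endpoint combines reaching 'no problem' with staying there. At stake are the precision of five comparisons for each of two doses, and a clear reading of what the percentages mean.

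**Working it through.** **The plan's own figure.** The SAP states no power for the EQ-5D-5L items. Its only power statement (Section 5.2) is for SRI-4: 40% versus 57%, two-sided 0.05, about 750 patients randomised 1:1:1, hence 250 per arm. A two-proportion calculation gives 96.9%, which agrees with the stated figure of more than 90%. This point does not affect it.

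**Inputs.** From the SAP: 250 per arm and a nominal 0.05. Assumed, because the SAP does not give them:
- b, the share at 'no problem' at baseline;
- s, the probability that such a patient is a 'no problem' responder at Week 52;
- r, the probability that a patient with a baseline problem reaches 'no problem'.

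**Composition of placebo responders.** The share who started at 'no problem' is b·s / (b·s + (1−b)·r).
- b = 0.20, s = 0.70, r = 0.20: 0.14 / (0.14 + 0.16) = 47%.
- b = 0.40, s = 0.75, r = 0.20: 0.30 / (0.30 + 0.12) = 71%.
- b = 0.60, s = 0.80, r = 0.20: 0.48 / (0.48 + 0.08) = 86%.

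The share passes one half at b = r / (s + r). For s from 0.65 to 0.90 and r from 0.10 to 0.40, that point lies between 10% (0.10/1.00) and 38% (0.40/1.05).

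**Noise from chance imbalance.** The standard deviation of the between-arm difference in b is √(2b(1−b)/250). At b = 0.40 this is √(0.48/250) = 4.4 points. Multiplied by s − r = 0.55, it moves the observed Week 52 difference by about 2.4 points.

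**Power without and with the baseline item.** Logistic regression, Wald test at 0.05, 250 per arm.

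Odds ratio 1.8 in all patients (2,000 trials per scenario):

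| b | s / r on placebo | Without | With | Gain (points) |
|---|---|---|---|---|
| 20% | 0.70 / 0.20 | 75% | 81% | 6 |
| 40% | 0.75 / 0.20 | 65% | 78% | 13 |
| 50% | 0.80 / 0.20 | 57% | 75% | 18 |
| 60% | 0.80 / 0.20 | 54% | 71% | 17 |

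A repeat of this setting gave gains of about 7 to 19 points.

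Effect set separately by baseline status, with 20% versus 34% reaching 'no problem' (1,500 trials per scenario). The last column restricts the analysis to patients with a baseline problem:

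| b | Effect on staying at 'no problem' | Without | With | Gain (points) | Restricted |
|---|---|---|---|---|---|
| 20% | none (75% both arms) | 72.5% | 81.0% | 8.5 | 88.6% |
| 40% | none | 49.3% | 58.3% | 9.0 | 80.7% |
| 60% | none | 23.5% | 28.1% | 4.6 | 60.1% |
| 20% | 65% versus 78% | 91.0% | 94.5% | 3.5 | 91.0% |
| 40% | 65% versus 78% | 85.9% | 93.6% | 7.7 | 77.1% |
| 60% | 65% versus 78% | 85.2% | 91.5% | 6.3 | 59.6% |

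**No drug effect.** Rejection without the baseline item was 5.1% (b = 30%) and 6.5% (b = 60%); with it, 5.5% and 5.3%. Simulation error is about 0.6 points, so type I error is near 5% either way.

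**Limit of the simulation.** The 'without' model leaves out the SAP's three stratification factors and the Firth penalty. If those factors predict the baseline item, the real gain would be somewhat smaller.

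**The case against.** The strongest reply is that nothing here is wrong in the SAP. A Week 52 state is a legitimate endpoint. LLDAS, a major secondary endpoint, is also a state, analysed without a baseline-status subset or covariate. Adjusting every logistic model for the stratification factors is a uniform convention. The baseline-adjusted index and VAS analyses already serve the stated EQ-5D-5L objective. All of this stands, and it limits the point to an improvement in efficiency.

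Three stronger readings are tempting, and the SAP does not support them.

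- **That these endpoints mostly measure where patients started.** This needs the baseline share at 'no problem' for each item, which the SAP does not give. At an assumed share of 20%, the first scenario above gives 47%, which is less than half. In any case, the make-up of the responders is not the treatment contrast.
- **That the comparison is biased.** Randomisation balances the baseline item in expectation, and the planned p-value and confidence interval already allow for chance imbalance. Adjustment would reduce that noise; it does not correct a bias.
- **That a patient at 'no problem' at baseline is automatically a responder.** The patient must also be at level 1 at Week 52 with non-missing data. In the PP datapoint set, data after treatment discontinuation, study discontinuation or prohibited medication count as missing. Staying at 'no problem' on those terms is something a drug can influence.

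Nor is restriction to patients with a baseline problem a clear replacement. It asks a different question. Where the drug also helps patients stay at 'no problem', it lowers power below the plan: 85.9% to 77.1% at b = 40%, and 85.2% to 59.6% at b = 60%.

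**Conclusion.** The point holds as a loss of precision. The item analyses use a Week 52 state in the whole mITT population and omit a baseline variable that is already collected and whose counterpart is used in the adjacent EQ-5D analyses. Adding it raised simulated power in every scenario with a drug effect, by roughly 4 to 19 points, and left type I error near 5%.

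The size rests on assumed baseline shares of 20% to 60%, on assumed rates of staying at and reaching 'no problem', and on 250 patients per arm. Gains are largest when the odds ratio applies to all patients and the baseline share is high. They are smaller, about 4 to 9 points, in the scenarios with the effect set separately by baseline status.

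Severity is low. These are other secondary endpoints, tested at a nominal 0.05 outside the multiplicity procedure; the primary and major secondary endpoints are untouched.

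**What to change.** In Table JAIA.6.6, add a footnote to the EQ-5D-5L item row saying that each of the five logistic models also includes the patient's baseline level of the same item (no problem versus any problem). Give a rule for a missing baseline item, such as a separate missing category, so that no mITT patient drops out of the model. Describe the endpoint as a Week 52 state that includes both reaching and maintaining 'no problem'.

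The proportion reaching 'no problem' among patients with a problem on that item at baseline may be added as a supplementary descriptive result, in the style of footnotes b, d and f. It should not replace the main row.

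The reported odds ratio would then be conditional on the baseline item and should be labelled so. The observed percentages and their Newcombe-Wilson differences stay as planned.

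The cost is one covariate already in the database, one footnote and a missing-baseline rule, with no new data. The change should be fixed before unblinding; if made later, it should be reported as an additional analysis.

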5.2 Determination of Sample Size

Study JAIA will randomize approximately 750 patients with a 1:1:1 ratio between baricitinib 4-mg, 2-mg, and placebo. The proposed sample size will ensure >90% power to detect an absolute difference of 17% between a baricitinib treatment group and the placebo treatment group assuming a 40% placebo response rate for the primary endpoint using a 2-sided α of 0.05. The anticipated effect size represents a clinically relevant difference.

Sample size and power estimates were obtained from nQuery® Advisor 7.0 using the χ^2 test of equal proportions.

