6.4.1 Adjustments for Covariates

Randomization is stratified according to disease activity (total SLEDAI-2K at screening <10; ≥ 10), corticosteroid dose at baseline (<10 mg/day; ≥ 10 mg/day prednisone or equivalent), and region (North America, Central/South America/Mexico, Europe, Asia and Rest of World). Therefore, these factors will be adjusted for as described in Section [6.4](#).

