6.9.1 Corticosteroid Dosing Conversion

To allow for assessments of changes in doses of various corticosteroids, all corticosteroid doses will be standardized to an equivalent prednisone dose. Table JAIA.6.3 provides a summary of frequent corticosteroids and their prednisone-equivalent dose. Given intramuscular injections (IM) are slow release, such injections will be divided by 7 and distributed across 7 days. This dose of corticosteroid will be referred to as “prednisone (or equivalent)” throughout this document.

Table JAIA.6.3. Conversion Factors for Calculating Prednisone (or Equivalent) Doses

Column 1	Column 2
Corticosteroid Preferred Name	Conversion Factor for Converting to an Equivalent Prednisone Dose
Prednisone	1
Prednisolone	1
Methylprednisolone	1.25
Triamcinolone	1.25
Cortisone	0.2
Hydrocortisone	0.25
Betamethasone	6.25
Dexamethasone	6.25
Paramethasone	2.5
Deflazacort	0.83

See [Appendix 1](#) for a complete table showing conversion factors for each corticosteroid medication identified during the study, instructions for selecting corticosteroids, and the manual review process.

Baseline prednisone (or equivalent) dose will be the total daily dose of all corticosteroids being taken by a patient on the day prior to the date of the first dose of study drug administration. This baseline dose will be used for baseline summaries and for comparisons to later visits. The corticosteroid dose for a postbaseline visit will be the daily dose of prednisone (or equivalent) at each visit date -1.

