Measure	Description	Variable	Derivation/Comment	Definition of Missing
Steroid sparing	This measures the proportion of patients who, having a high enough dose at baseline, are able to reduce steroids to a certain level.	Receiving >7.5 mg prednisone (or equivalent) at baseline and able to decrease dose by $\geq 25\%$ to a prednisone equivalent dose of ≤ 7.5 mg/day maintained between the Week 40 visit and the Week 52 visit	Dose reduction must be greater than or equal to baseline dose $\times .25$ and achieve a dose of less than or equal to 7.5 mg per day perpetually between the Week 40 visit and Week 52 visit.	No minimum data requirement.
		Receiving >7.5 mg prednisone (or equivalent) at baseline and able to decrease dose by $\geq 25\%$ by the Week 52 visit	Dose reduction must be greater than or equal to baseline dose $\times .25$ per day perpetually between the Week 40 visit and the Week 52 visit.	No minimum data requirement.
		Receiving >7.5 mg prednisone (or equivalent) at baseline and able to decrease to a prednisone equivalent dose of ≤ 7.5 mg/day by the Week 52 visit	Dose reduction must be less than or equal to 7.5 mg per day perpetually between the Week 40 visit and the Week 52 visit.	No minimum data requirement.
		Receiving prednisone (or equivalent) at baseline and able to discontinue and maintain through the Week 52 visit	Among patients with baseline prednisone (or equivalent) dose >0 mg and able to reduce the dose to 0mg at some time point and then maintained at 0mg from that time through the Week 52 visit.	No minimum data requirement.
Worst Joint Pain NRS	This Worst Joint Pain NRS is a single-item, patient-administered 11-point horizontal scale anchored at 0 (no joint pain) and 10 (joint pain as bad as you can imagine)	Worst Joint Pain NRS Score	Calculated by averaging data for all available daily diary entries for a 7-day period prior to the visit, not inclusive of the clinic visit day.	Missing if fewer than 4 available daily measurements in the relevant 7 days

Description and Derivation of Efficacy/Health Outcomes Measures and Endpoints

Measure	Description	Variable	Derivation/Comment	Definition of Missing

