Corticosteroid Sparing	Proportion of patients receiving > 7.5 mg/day prednisone at baseline able to reduce prednisone (or equivalent) dose by $\geq 25\%$ to a prednisone equivalent dose of ≤ 7.5 mg/day maintained between Week 40 and Week 52 visit ^g	Logistic Regression, NRI + mLOCF	PPCV	Week 52 visit	Major secondary (Principal inference)
		Logistic Regression, NRI	PP		Supplemental
		Logistic Regression, NRI	AC		Supplemental
	Proportion of patients receiving > 7.5 mg/day prednisone at baseline able to reduce prednisone (or equivalent) dose by $\geq 25\%$ maintained between Week 40 and Week 52 visit ^g	Logistic Regression, NRI + mLOCF	PPCV	Week 52 visit	Supplemental
		Logistic Regression, NRI	PP		Supplemental
	Proportion of patients receiving > 7.5 mg/day prednisone at baseline able to reduce prednisone (or equivalent) dose to ≤ 7.5 mg/day maintained between Week 40 and Week 52 visit ^g	Logistic Regression, NRI + mLOCF	PPCV	Week 52 visit	Supplemental
		Logistic Regression, NRI	PP		Supplemental
	Change from baseline in prednisone dose	MMRM	PP	Week 52 visit	Secondary endpoint
	Proportion of patients able to discontinue corticosteroids and maintained through Week 52 visit ^h	Logistic Regression, NRI	PP	Week 52 visit	Secondary endpoint
Worst Pain NRS	Change from baseline in Worst Pain NRS	MMRM+MI	PPCV	Week 52 visit	Major secondary (Principal inference)
		MMRM	PP		Supplemental
		MMRM	AC		Supplemental

Description of Efficacy/Health Outcomes Analyses

Measure	Variable	Analysis and Imputation Method	Datapoint Sets	TPI*	Analysis Type
FACIT-Fatigue	Change from baseline in FACIT-Fatigue total score	MMRM+MI	PPCV	Week 52 visit	Major Secondary (Principal inference)
		MMRM	PP		Supplemental
		MMRM	AC		Supplemental
Worst Fatigue NRS	Change from baseline in Worst Fatigue NRS	MMRM	PP	Week 52 visit	Secondary endpoint
Worst Joint Pain	Change from baseline in Worst Joint Pain NRS	MMRM	PP	Week 52 visit	Secondary endpoint
Joint Stiffness Duration	Change from baseline in Joint Stiffness Duration	Wilcoxon rank-sum with mLOCF	PP	Week 52 visit	Secondary endpoint
Joint Stiffness Severity	Change from baseline in Joint Stiffness Severity	MMRM	PP	Week 52 visit	Secondary endpoint
Patient Global Impression of Severity	Change from baseline in Patient Global Impression of Severity	MMRM	PP	Week 52 visit	Secondary endpoint
Patient Global Impression of Change	Change from baseline in Patient Global Impression of Change	ANOVA with mLOCF	PP	Week 52 visit	Secondary endpoint

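### The steroid-sparing model omits baseline prednisone dose, although the cut needed to respond depends on it; adding it is a cheap, small gain

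*SAP*

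**What the plan says.** Table JAIA.6.6 (Section 6.10.1) lists three steroid-sparing responder endpoints in patients taking more than 7.5 mg/day prednisone at baseline. The one requiring both a cut of at least 25% and a dose of 7.5 mg/day or less is a major secondary endpoint with principal inference; the other two are supplemental. Footnote g gives all three their own model: "The logistic regression model covariates include treatment groups, baseline disease activity" (SAP, Section 6.10.1) and region. It has no steroid term, neither the <10/≥10 mg/day stratification factor nor the dose itself, and gives no reason.

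The response rule is in Table JAIA.6.4. The reduction must be at least a quarter of the baseline dose, and the patient must "achieve a dose of less than or equal to 7.5 mg per day perpetually" between the Week 40 and Week 52 visits.

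Elsewhere the SAP does adjust for baseline steroid use:

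- Section 6.4 introduces the default binary model with "For assessments of the primary endpoint and other binary efficacy and health outcomes endpoints, the following will be provided unless otherwise specified"; that model contains the <10/≥10 mg/day factor.
- Section 6.4.1 says of the stratification factors: "Therefore, these factors will be adjusted for as described in Section" 6.4.
- "Change from baseline in prednisone dose" is analysed by MMRM, whose terms include "visit (as categorical variable), baseline value, treatment-by-visit interaction, and baseline value-by-visit interaction". For this outcome the baseline value is the baseline dose, and the <10/≥10 factor is there as well.
- The endpoint of stopping steroids altogether (footnote h) has no covariate list of its own, so the Section 6.4 default applies.

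Section 6.9.1 already derives the variable: "This baseline dose will be used for baseline summaries and for comparisons to later visits".

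**The concern.** The endpoint ties the required reduction to the starting dose. A patient on 10 mg/day must come down by a quarter; a patient on 40 mg/day must come down by about four fifths. Baseline dose is therefore likely to predict response strongly, and the model for the alpha-controlled endpoint ignores it. The continuous version of the same dose data is adjusted for it.

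The stakes are limited. Leaving out a prognostic covariate in a randomized comparison does not bias the test. It forgoes some power and leaves chance imbalance in dose unadjusted. That matters a little more here because the endpoint is tested in a subset of unstated size.

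**Working it through.** **1. The plan's own power figure.** Section 5.2 sizes the trial for the primary endpoint only, "assuming a 40% placebo response rate for the primary endpoint using a 2-sided α of 0.05", with a 17-point difference and about 750/3 = 250 patients per arm. A two-proportion calculation of 40% vs 57% gives 96.9% power; 180 per arm (192 with continuity correction) would give 90%. The stated >90% reproduces. No power or sample size is given for steroid sparing.

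**2. Required cut by baseline dose.** From Table JAIA.6.4, required cut = 1 - min(0.75, 7.5/dose). The 40 mg/day upper end is the permitted baseline maximum in Table JAIA.6.2.

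| Baseline dose (mg/day) | 8 | 10 | 12.5 | 15 | 20 | 30 | 40 |
|---|---|---|---|---|---|---|---|
| Required cut | 25% | 25% | 40% | 50% | 62.5% | 75% | 81.25% |

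In this subset the <10 stratum covers only doses above 7.5 and below 10 mg, where the required cut is the same 25% as at 10 mg. The binary factor therefore misses nearly all of the gradient.

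**3. Power with and without dose.** All inputs in this step are assumptions, because the SAP does not give them:

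- 100 or 125 patients per arm, 30% placebo rate, conditional log odds ratio 0.75, two-sided alpha 0.05.
- Base dose mix for 8/10/12.5/15/20/30/40 mg of 6/36/12/18/16/7/5%.
- Slope is the change in log odds per unit of natural-log dose. From 10 to 40 mg (ln 4 = 1.386), slopes of -1, -1.5 and -2 mean 4-, 8- and 16-fold falls in the odds of response.
- SLEDAI-2K and five regions are in every model, with no true effect.
- Allocation is 1:1 within the <10/≥10 mg strata; Firth logistic regression, Wald test, 10,000 runs per scenario.

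| Slope | 100/arm: without | with log dose | change | 125/arm: without | with log dose | change |
|---|---|---|---|---|---|---|
| 0 | 70.2% | 70.0% | -0.2 | 79.7% | 79.5% | -0.2 |
| -0.5 | 69.6% | 69.5% | -0.1 | 78.8% | 79.1% | +0.3 |
| -1 | 67.9% | 68.4% | +0.5 | 76.9% | 77.6% | +0.7 |
| -1.5 | 64.0% | 65.9% | +1.9 | 73.7% | 76.0% | +2.3 |
| -2 | 59.7% | 63.8% | +4.1 | 70.9% | 75.2% | +4.3 |

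The paired standard error of each change is 0.1 to 0.34 points.

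**4. Sensitivity.** Over four dose mixes and placebo rates of 20-40%, the change in points is:

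| Slope | Range of change |
|---|---|
| 0 (four mixes only) | -0.3 to -0.2 |
| -0.5 | -0.2 to +0.3 |
| -1 | +0.1 to +1.5 |
| -1.5 | +0.8 to +3.0 |
| -2 | +1.7 to +4.9 |

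The <10/≥10 factor alone changes power by -0.5 to -0.1 points when 6% of patients are below 10 mg, and by -0.3 to +1.3 when 25% are.

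A second set of runs used other assumptions: about half the subset at 10 mg, log odds ratio 0.8, 1,500 runs, slope per doubling of dose. Since ln 2 = 0.693, slopes of -0.7, -1.4 and -2.2 per doubling are about -1.0, -2.0 and -3.2 per natural log.

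| Slope per doubling | 110/arm: without → with | 75/arm: without → with |
|---|---|---|
| 0 | 79.4 → 78.8% | 61.7 → 61.7% |
| -0.7 | 76.3 → 77.9% | 61.5 → 62.0% |
| -1.4 | 73.5 → 76.5% | 53.9 → 56.7% |
| -2.2 | 63.5 → 70.3% | 48.0 → 53.6% |

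With 1,500 runs a single power figure has a standard error of about 1 point (sqrt(0.79 × 0.21/1500) = 0.0105). The pattern is the same: about 0 to 3 points, and 6 to 7 only in the extreme case.

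**5. Type I error.** In the 10,000-run scenarios it is 4.2-4.9% without dose and 4.3-4.8% with it; in the smaller set, 3.2-5.7% over both models. Neither model shows inflation.

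**6. Chance imbalance.** The SD of log dose within strata is about 0.40 in the base mix. At 100 per arm the 95% range of the difference in mean log dose is ±1.96 × 0.40 × sqrt(2/100) = ±0.11. At slope -1 the edge of that range moves the odds ratio by a factor of exp(0.11) = 1.12. The unadjusted standard error already covers this variation.

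**The case against.** The strongest reply is that nothing is wrong. Section 6.4 lets an endpoint specify its own model and footnote g does so. The test is valid, and dropping a <10/≥10 factor that is nearly empty in this subset is sensible. The MMRM comparison is weak, because a baseline value enters every change-score model by a generic rule, and no binary endpoint in the SAP has a continuous baseline covariate. The gain is negligible unless response odds fall steeply with dose, and the SAP supplies no slope. Non-response imputation after discontinuation or prohibited medication could flatten the slope, and SLEDAI-2K or region may already carry part of the dose effect. The alpha for this endpoint comes from a graph that is not reproduced in the available text, so 0.05 is itself an assumption. Log-linear dose is only approximate, because the required cut is flat up to 10 mg.

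Most of this stands, and it is why the point is optional. It does not remove the case for the covariate. A near-empty binary factor explains dropping that factor, not leaving out the dose. The dependence of the required cut on dose follows from the endpoint definition and needs no assumed slope. On functional form, with a true effect flat below 10 mg the log-linear term still gained 0.6 points at slope -1 and 4.0 at -2.

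One further point is fair: adding a prognostic covariate changes the conditional odds ratio being estimated. In the second set of runs at 110 per arm, the mean log odds ratio was 0.74 without dose and 0.81 with it at -1.4 per doubling, and 0.67 and 0.80 at -2.2. This is non-collapsibility, not correction of a bias, and the report should say which odds ratio it gives.

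**Conclusion.** The concern holds as a minor, optional improvement. Footnote g leaves out a baseline variable on which the response rule itself depends, in an alpha-controlled analysis of a subset. The consequence is a small loss of efficiency: roughly nil for a flat or shallow dose effect, up to about 1.5 points for a moderate one (slope -1), and about 2 to 5 points for a steep one (slope -2) over the main scenarios. These sizes rest on assumed subset size, response rate, dose mix, slope and alpha. The structural point does not. There is no bias, no type I inflation and no contradiction in the SAP, and the stated power for the primary endpoint is unaffected.

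**What to change.** In footnote g, add baseline prednisone-equivalent dose, continuous on the log scale, to the Firth logistic model for the two endpoints that require 7.5 mg/day or less. For the supplemental endpoint that requires only a 25% cut, the required percentage does not vary with dose, so inclusion there is optional and serves only to keep one common model. Restoring the <10/≥10 factor instead is not an adequate substitute. A sentence in Section 6.4.1 noting that footnote g endpoints use their own covariate set would be a helpful clerical addition, no more.

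The cost is one covariate in one footnote; the variable already exists. If dose turns out not to be prognostic, the extra parameter cost 0.2 to 0.3 points of power in the 10,000-run scenarios; allow up to about 0.5. The change should be made only before unblinding. After that, the dose-adjusted model belongs among the supplementary analyses, labelled as post hoc.
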